3.4.2 Exploratory pharmacodynamic endpoints

Goal: Analyze change from baseline (V2; day1) in levels of lipoproteins and apolipoproteins in CSF and plasma, AD biomarkers in CSF and plasma at day 84 (V4) and EOT (V6; day 168).

Variables:

- Lipoproteins and apolipoproteins in plasma: LDL-C, total cholesterol, non-HLD-C, triglycerides and ApoB
- Lipoproteins and apolipoproteins in CSF and plasma: HDL-C, HDL-ApoE, and ApoA2
- AD biomarkers in CSF: pTau181, Ab42, Ab40, Ab42/40, NRGN, GFAP, sTREM2, YKL-40, and inflammatory cytokines
- AD biomarkers in plasma: pTau epitopes, Ab42, Ab40, Ab42/40, and NFL
- Lipids in CSF and plasma: 24-OHC, 27-OHC, desmosterol, lathosterol, campesterol, and sitosterollnoviv proteins CSF: ApoB (1 peptide), Clusterin (3 peptides)

Methods:

In case of CSF measurements, the Wilcoxon signed rank test will be performed between baseline and EOT. The measurements of V4 are not taken into consideration for the analysis.

The Friedman test will be used on the plasma samples to determine if there is a significant difference in any of the variables at the three time-points. Post-hoc analysis will include Wilcoxon signed rank test between Baseline and Day 84 and Baseline and EOT. A Bonferroni multiple testing correction will be applied at alpha-level 0.05 for multiple testing within the same variable. Post hoc analysis will only be performed on the patients who have all 3 measurements available.

3.4.3 Correlation analysis

Goal: Perform correlation analysis between the change from baseline levels in CSF pTau181 and CSF ApoA1, ApoE, and cholesterol efflux capacity

Variables:

- CSF pTau181
- CSF ApoA1
- CSF ApoE
- CSF cholesterol efflux

Methods: Use rate of change between V1 (baseline) and V6 (day 168; EOT) for each of the variables mentioned above. Only participants who have both time points available will be included in the analysis.

A Spearman's rank correlation analysis will be performed. Correlation is significant if p<0.05. If the correlation coefficient is ≥ 0.7 there is a strong correlation, a correlation coefficient $\geq 0.5 < 0.7$ is moderate, and $\geq 0.3 < 0.5$ is low.

3.4.4 Exploratory cognition endpoints

Variables:

- CFC
- MMSE

Methods:

The Friedman test will be used to test if there is an overall difference. Significant if p<0.05. Post-hoc analysis will include Wilcoxon signed rank test between Baseline and Day 84 and Baseline and EOT. A Bonferroni multiple testing correction will be applied at alpha-level of 0.05 for multiple testing within the same variable.

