6.1.3 Visit 4 (Day 84 \pm 6 Days)

All patients returning for Visit 4 (Day 84 ± 6 days) will undergo the following procedures:

- Recording of vital signs;
- Physical and neurological examination;
- Documentation of AEs and concomitant medications;
- Administration of the Columbia-Suicide Severity Rating Scale (C-SSRS);
- Administration of MMSE;
- Fasting (~10 hours) blood sampling for clinical chemistry and PD and PK parameters (see Section 7).
- Optional: performing of lumbar puncture for CSF sample (see Section 7);
- Study drug compliance check; and

Patients will receive a supply of study drug with instructions on how to take it. Patients will be given an appointment to return with all used and unused study drug at Day 126 (± 6 days).

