6.1.5 End of Treatment Visit 6 (Day 168 \pm 6 Days)

All patients returning for Visit 6 (Day 168 \pm 6 days) will undergo the following procedures:

- Recording of weight;
- Recording of vital signs;
- Performing 12-lead ECG;
- Fasting (~10 hours) blood sampling for hematology, clinical chemistry, and PD and PK parameters (see Sections 7 and 8.7);
- Collection of urine sample for urinalysis;
- Physical and neurological examination;
- Documentation of AEs and concomitant medication;
- Administration of the Columbia-Suicide Severity Rating Scale (C-SSRS);
- Administration of MMSE and CFC;
- Performing of lumbar puncture for CSF sample; and
- Study drug compliance check

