At Baseline (Visit 2), at Day 84 (Visit 4), and the End of Treatment (Day 168, Visit 6), the following parameters will be measured in the plasma:

- Tau and p-Tau epitopes
- $A\beta_{1-42}$, $A\beta_{1-40}$, $A\beta_{1-42}/A\beta_{1-40}$ ratio
- Neurofilament light

Correlation Between the Change From Baseline Levels in CSF p-Tau 181 and CSF ApoA-I, ApoE, and Cholesterol Efflux Capacity

At Screening (Visit 1) and at the End of Treatment (Day 168, Visit 6), p-Tau 181, ApoA-I, ApoE, and cholesterol efflux capacity will be measured in the CSF.

Change From Baseline Levels in 24-Hydroxycholesterol and 27-Hydroxycholesterol in CSF and Plasma

At Baseline (Visit 2), Day 84 (Visit 4), and the End of Treatment (Day 168, Visit 6), 24-hydroxycholesterol and 27-hydroxycholesterol will be measured in the CSF and plasma samples.

Note, CSF sampling for 24-hydroxycholesterol and 27-hydroxycholesterol in CSF at Day 84 (Visit 4) is optional.

Exploratory Cognition Endpoints

Disease Progression Measured With the Cognitive-Functional Composite

At Baseline (Visit 2) and the End of Treatment (Day 168, Visit 6), the CFC test will be administered to allow tracking of disease progression.

The CFC test was designed to improve the measurement of progression in early dementia stages of AD by providing a short and clinically relevant measure focusing on the cognitive domains and activities of daily living that are sensitive to decline in early AD.

The CFC combines the Short Version of the Amsterdam Instrumental Activities of Daily Living Questionnaire (A-IADL-Q-SV) and a brief neuropsychological test battery focusing on episodic memory and executive functions^{29,30}. The psychometric quality of the CFC was evaluated in the Catch-Cog study; an international, multi-center, independent longitudinal validation study including individuals with MCI and mild dementia due to AD²⁹. The CFC was found to have good test-rest reliability, and patients and caregivers experienced the content of the CFC as relevant and the administration as user-friendly^{30,31}. Further, it was shown that the CFC has good construct validity and quality for the target population, as evidenced by associations with clinical and biological measures of disease severity^{32,33}, and limited range restrictions in scoring at baseline³³.

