2.3.3 Exploratory cognition endpoints

Disease Progression Measured With the Cognitive-Functional Composite

At Baseline (Visit 2) and the End of Treatment (Day 168, Visit 6), the CFC test will be administered to allow tracking of disease progression.

Mini-Mental State Examination

At Screening (Visit 1), Baseline (Visit 2), Day 84 (Visit 4), and the End of Treatment (Day 168, Visit 6), the MMSE will be administered.

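### SAP 3.4.4 applies a three-visit test procedure to the CFC, which is measured at only two visits: the Day 84 contrast has no data and the Friedman test becomes a sign test

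*SAP*

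**What the plan says.** SAP 3.4.4 lists CFC and MMSE as its variables and gives a single method without separating them. The overall test is stated as "The Friedman test will be used to test if there is an overall difference", with significance at p<0.05. It continues: "Post-hoc analysis will include Wilcoxon signed rank test between Baseline and Day 84 and Baseline and EOT". On multiplicity it says: "A Bonferroni multiple testing correction will be applied at alpha-level of 0.05 for multiple testing within the same variable".

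The timing of the CFC is set out in SAP 2.3.3: "At Baseline (Visit 2) and the End of Treatment (Day 168, Visit 6), the CFC test will be administered". Protocol Section 7 gives the same two visits. The protocol's visit lists agree. For cognition, Visit 4 (Day 84) has only "Administration of MMSE", while Visit 6 (Day 168) has "Administration of MMSE and CFC". The schedule tables in Protocol Appendix A and SAP Table 1 also mark the CFC at V2 and V6 only. The MMSE is given at Screening, Baseline, Day 84 and Day 168.

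SAP 3.1.4 rules out imputation for the cognitive endpoints.

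**The concern.** The procedure in SAP 3.4.4 assumes three repeated measurements. The MMSE has them and the CFC does not. Three things follow for the CFC:

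- One of its two stated contrasts, Baseline to Day 84, has no scheduled pairs.
- Its overall test is run on two time points. There the Friedman test uses only the direction of each patient's change, so it is a different and usually weaker test of the same Baseline-to-Day-168 comparison that the Wilcoxon test addresses.
- The decision rule is unclear. The Bonferroni divisor could be one or two, and the Wilcoxon test may or may not depend on a significant Friedman result.

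The CFC is one of only two cognition endpoints, and the one the SAP describes as measuring disease progression. In an open-label study, a rule left open can be settled after the data have been seen.

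**Working it through.** **Inputs.** CFC visits are V2 and V6 (SAP 2.3.3; Protocol Section 7; both schedule tables). The sample is 10 to 15 patients in one arm (SAP 2.2.4). Nominal alpha is 0.05, Bonferroni-corrected within a variable (SAP 3.4.4). Sidedness is not stated, so two-sided is assumed. The documents give no effect size, SD or completer count for the CFC, so there is no planned figure to reproduce.

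**Day 84 contrast.** There are no scheduled CFC pairs, and imputation is excluded. An early termination visit follows the Visit 6 procedures, and no SAP rule maps it to Day 84.

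**Friedman with two time points.** Let S be the number of patients, out of n, whose score rises. With no ties the statistic is

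Q = (2S − n)² / n, referred to chi-square with 1 df.

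With ties it is (n₊ − n₋)² / (n₊ + n₋), where n₊ and n₋ count rises and falls. The identity held exactly in 2,000 random data sets with ties. This is the uncorrected large-sample sign test.

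**True size.** The SAP names no reference distribution; the usual chi-square is assumed. Rejection needs Q > 3.841. For n=12 that means at least 10 patients changing in the same direction: Q = (20 − 12)²/12 = 5.33, and the two-sided size is 2 × (66 + 12 + 1)/4096 = 0.0386.

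| n | Same direction needed | True size at nominal 5% |
|---|---|---|
| 10 | 9 | 2.1% |
| 11 | 9 | 6.5% |
| 12 | 10 | 3.9% |
| 13 | 11 | 2.2% |
| 14 | 11 | 5.7% |
| 15 | 12 | 3.5% |

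The size exceeds 5% at n=11 and n=14. With exact binomial p-values, the thresholds there rise to 10 and 12, and size over n=10 to 15 lies between 1.2% and 3.9%.

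**How the readings can disagree.** Take n=12 with changes of +4 to +12 in nine patients and −1, −2, −3 in three.

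- Friedman: Q = (18 − 12)²/12 = 3.0, p = 0.083.
- Wilcoxon: the negative ranks sum to 1 + 2 + 3 = 6. Of the 4096 sign patterns, 14 give a sum of 6 or less, so p = 2 × 14/4096 = 0.0068.

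On the same data the overall test fails, while the Wilcoxon test passes at either 0.05 or 0.025.

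**Illustrative power.** Assumptions: normally distributed changes, mean 0.8 SD, exact Wilcoxon test; 200,000 simulated trials per cell, figures good to about one percentage point.

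| Reading of the CFC rule | n=10 | n=12 | n=15 |
|---|---|---|---|
| One Wilcoxon at 0.05 | 60% | 67% | 80% |
| Wilcoxon at 0.025, no gate | 41% | 54% | 68% |
| Friedman alone | 34% | 52% | 60% |
| Friedman, then Wilcoxon at 0.025 | 30% | 45% | 56% |

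The Friedman-based rows do not rise steadily with n, because the test is so discrete. They peak at n=14 (66% and 58%). At n=12, the first row against the last is 32% vs 17% for a 0.5 SD change and 95% vs 82% for 1.2 SD.

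**The case against.** The strongest reply is that only one element is void. A programmer would drop the Day 84 contrast for lack of data, and the Baseline-to-end-of-treatment Wilcoxon test is already in the text. With one contrast left there is no multiple testing within the variable, so the natural Bonferroni divisor is one. Calling the Wilcoxon tests post hoc to an overall test implies a hierarchy. On that reading the 0.025 comparisons overstate the problem. The power figures also rest on assumed normal changes, which favour the Wilcoxon test over a sign test, and the gap depends heavily on n: at n=11 and 0.8 SD, Friedman alone has about 58% against 62% for Wilcoxon at 0.05.

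Much of this is fair. A divisor of one is the more natural reading, the power figures are illustrative only, and the unstated gate is not peculiar to the CFC: it applies equally to the MMSE and to the plasma markers in SAP 3.4.2. None of it removes the mismatch. The text contains no exemption for the CFC, and a gate, if intended, would make a two-point sign test decide whether the Wilcoxon test of the same comparison counts.

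A second objection is that a single ungated Wilcoxon test at 0.05 is the most permissive reading, chosen late: SAP version 4.0 is dated 28 November 2023 and the study is open-label. That stands, and the timing of the choice should be disclosed.

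**Conclusion.** The concern holds. SAP 3.4.4 prescribes for the CFC a contrast with no data and an overall test that reduces to a large-sample sign test with a true size between 2.1% and 6.5% at n=10 to 15 (chi-square reference, no ties). This is an error in the rule as written, not merely missing detail. That the Friedman and Wilcoxon results can conflict follows from arithmetic alone. How much power is lost depends on the assumed effect and on which reading is adopted.

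Severity is minor. The CFC is exploratory, the study is uncontrolled, and descriptive summaries will be available whichever test is used.

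**What to change.** Separate the two variables in SAP 3.4.4.

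- **CFC:** test the change from V2 to V6 with one Wilcoxon signed rank test at two-sided 0.05, with no Friedman test and no Bonferroni factor. SAP 3.4.2 already takes this approach for two-point data: "In case of CSF measurements, the Wilcoxon signed rank test will be performed between baseline and EOT".
- **MMSE:** keep the Friedman test and the two contrasts at 0.025 each (0.05/2), and state whether the contrasts require a significant Friedman result.

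The cost is about two sentences, with no new data or visits. Results tables must label the different procedures for the two endpoints. Because this settles an open choice late in an open-label study, the SAP should record when it was made relative to database lock and to any look at the CFC data. If the analysis has already been run, the clinical study report should state which rule was applied and present any change as a deviation, as SAP Sections 1 and 5 require.

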3.5 Pharmacokinetic assessment

Pharmacokinetic (PK) assessments will be performed on the PP population. PK values will be summarized using descriptive statistics per visit per matrix (CSF and blood).

3.6 Safety assessment

The Safety Population will be the primary population for the safety analyses. All safety endpoints will be summarized descriptively. No statistical inference will be applied to the safety endpoints.

AEs will be categorized by primary system organ class and preferred term as coded using the Medical Dictionary for Regulatory Activities (MedDRA) category designations. Summaries of AEs, including the number and percentage of patients who experience an AE, will be provided.

Laboratory values will be summarized descriptively, including the change from baseline. In addition, shift tables will be presented to describe the change in laboratory parameter values at post-baseline visits using normal range categories (low, normal, and high).

Vital signs will be summarized descriptively, including the change from baseline.

ECG results, as well as physical and neurological examination findings will be listed. Clinically relevant abnormal findings at baseline or during the study will be reported as baseline condition or AE, respectively.

4. Analysis timing

4.1 Interim analysis

No interim analysis was planned for this study.

4.2 Final analysis

After the study database is declared final, the final analysis will be generated. Final TFLs will be provided approximately one week after receival of all endpoint assessments.

5. Changes from protocol-specified statistical analysis

This SAP deviates from the statistical analysis described in v2.0 of the protocol. In the protocol it is stated that only descriptive statistics will be included and no formal hypothesis will be tested in the study. However, here we show several statistical analysis which are based on hypothesis testing.

Any deviations from the SAP will be described in the CSR.

6. Programming specifications

Analyses will be performed using R version 4.2.1 All available data will be presented in participant data listings which will be sorted by participant and visit date as applicable. Detailed Programming Specifications will be provided in a separate document.

Appendix A: Clinical laboratory analytes

Chemistry Panel

Alanine aminotransferase (ALT)

Albumin

Alkaline phosphatase

Aspartate aminotransferase (AST)

Blood urea nitrogen

Albumin

Amylase

Bicarbonate

Calcium

Chloride Creatine kinase (CK)

Creatinine Estimated glomerular filtration rate (eGFR)

[1]

Folic acid [2] Gamma-glutamyl transferase

Glucose (fasting) High-sensitivity C-reactive protein

Inorganic phosphorus Lactate dehydrogenase

Lipase Potassium

Sodium Thyroid stimulation hormone (TSH) [2]

Thyroxine (T4) [2] Total bilirubin

Total protein Triiodothyronine (T3) [2]

Uric acid Vitamin B12 [2]

[1] Calculated using the Chronic Kidney Disease Epidemiology Collaboration equation: https://www.mdcalc.com/ckd-epi-equations-glomerular-filtration-rate-gfr.

[2] Screening Visit only.

Endocrinology

Follicle-stimulating hormone – At screening visit only for women <55 years of age

Hematology

Hemoglobin A1c (HbA1c) [1] Hematocrit

Hemoglobin International normalized ratio (INR)

Partial thromboplastin time (PTT) Platelets

Prothrombin time (PT) Red blood cell count
White blood cell count and differential [2] APOE E4 genotyping [1]

[1] Screening Visit only.

[2] Manual microscopic review is performed only if white blood cell count and/or differential values are out of reference range.

Urinalysis

Bilirubin Blood Glucose Ketones

Leukocyte esterase Microscopy [1]

Nitrite pH

Protein Specific gravity

Urobilinogen

[1] Microscopy is performed only as needed based on positive dipstick test results

Pregnancy Test

Urine – At screening and V6 for women <55 years of age

Pharmacodynamic parameters

CSF:

- ApoA-I, ApoE, small HDL particles and ABCA1-driven cholesterol efflux, HDL-C, HDL-ApoE, ApoA-II
- YKL40
- sTREM2
- 24-hydroxycholesterol and 27-hydroxycholesterol

- Tau and p-Tau 181, Aβ₁₋₄₂, Aβ₁₋₄₀, Aβ₁₋₄₂/Aβ₁₋₄₀ ratio, neurogranin, neurofilament light, GFAP
- Inflammatory markers (eg, IFN-γ, IL-10, IL-12p70, IL-17A, IL-6, TNF-α)

Plasma:

- TC, ApoA-I, ApoE, ApoB, LDL-C [1], Non-HDL-C, TG, small HDL particles and HDL-C, HDL-ApoE, ApoA-II
- 24-hydroxycholesterol and 27-hydroxycholesterol
- Tau and p-Tau epitopes, $A\beta_{1-42}$, $A\beta_{1-40}$, $A\beta_{1-42}/A\beta_{1-40}$ ratio, neurofilament light

^[1] Measured by preparative ultracentrifugation, also referred to as beta quantification.
